4.3.3 Exploratory Efficacy Endpoints

Exploratory efficacy analyses endpoints will include the following:

- Initial (primary) QFT conversion using an alternative definition of QFT positive/negative derived based on a concentration cut-off value of 4 IU/mL in the QFT assay similarly to the procedure described in Table 1 for the 0.35 IU cut-off (initial conversion only). Primary (initial) QFT conversion corresponds to the first QFT conversion from a negative to positive test result. This endpoint will be evaluated using the mITT analysis population (Section 5.1) at the time of the primary analysis, the secondary analysis, and at the final analysis.
- Initial (primary) and sustained QFT conversion for various thresholds ranging from 0.36 IU/mL to 10 IU/mL. Each threshold cut-off will be used to assess initial conversion similarly to the procedure described in Table 1 for the 0.35 IU cut-off. Sustained conversions for the various thresholds will be a subset of the sustained converters identified for the primary endpoint for which the initial conversion is assessed based on

the various threshold values. Both initial (primary) and sustained QFT conversions based on various thresholds will be evaluated using the mITT analysis population (Section 5.1) at the time of the primary analysis, the secondary analysis, and at the final analysis.

- End of trial sustained conversion defined as QFT conversion from a negative to positive test result (as per the manufacturer's QFT-GIT package insert) any time post Day 71 with all QFT results after the initial conversion also positive. This endpoint will be evaluated using mITT analysis population (Section 5.1) at the time of the final analysis.
- Early QFT Reversion is defined as QFT reversion from a positive to a negative test result at the post conversion Day 84 visit and/or at the biannual visit following initial conversion. This endpoint (rate of Early QFT Reversions) will be evaluated using the mITT analysis population (Section 5.1) at the time of the primary analysis.

A subset of the exploratory efficacy analyses may be performed at the time of the primary analysis (Section 4.2.2) and at the time of the secondary analysis (Section 4.2.3). These will be identified prior to database freeze and/or unblinding for the respective analyses.

All other exploratory objectives (e.g., related to immunogenicity or biomarkers) will be analyzed by Gates MRI. No details of these analyses of these objectives are described within this SAP. Specific objectives and hypotheses related to these analyses will be documented and reported in a separate scientific and statistical analysis plan(s), and results documented outside the clinical study report (CSR).

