• To evaluate the efficacy and durability of efficacy of BCG revaccination against primary Mtb infection post vaccination versus placebo in previously BCG vaccinated, QFT negative healthy adolescents	 Primary QFT conversion at the time of primary endpoint analysis, and after a follow-up of 36- and 48-months post vaccination, using an alternative definition of conversion as a change in IFN-γ concentration from <0.35 IU/mL to ≥4 IU/mL (initial conversion only) 		
 To evaluate the efficacy and durability of efficacy of BCG revaccination against primary and sustained Mtb infection post vaccination versus placebo in previously BCG vaccinated, QFT negative healthy adolescents, based on alternate QFT IFN-γ concentration cut-off values 	 Primary and sustained QFT conversion at the time of primary endpoint analysis, and after a follow-up of 36- and 48-months post vaccination, based on a definition of primary and sustained conversions using exploratory IFN-γ concentration threshold values 		

Objectives	Endpoints	
Exploratory, continued		
To assess the immunogenicity of BCG revaccination	 Frequency of Mtb-, BCG- and/or non-tuberculous mycobacteria (NTM)-specific cluster of differentiation (CD)4 T cells expressing one or more cytokines, e.g., IFN-γ, tumor necrosis factor (TNF)-α, interleukin (IL)-2 and/or IL-22 by intracellular cytokine staining (ICS) 	
 To describe host attributes and host responses to vaccination To describe host attributes and host responses following QFT conversion To explore and/or develop candidate correlates of risk (CoRs) and correlates of protection (CoPs) To detect and describe incident TB disease To characterize Mtb isolates 	 Endpoints may include: Genetic markers and sequences Transcriptomics and gene expression markers Proteomics Antibody analyses Cellular analyses (eg, natural killer cells [NK cells], B cells, T cells, myeloid cells) 	
• To describe COVID-19 among study participants who present with suspected COVID-19	 Signs and symptoms of illness, by treatment group SARS-CoV-2 nucleic acid amplification from nasal or oropharyngeal sample 	
• To describe the serostatus of SARS-CoV-2 infection	• Serological tests for SARS-CoV-2, by treatment group	

Refer to Section 7.4 for COVID-19 Pandemic contingency plans.

4. Study Design

Overall Design:

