6 CHANGES IN CONDUCT OR PLANNED ANALYSES FROM THE PROTOCOL

ITT efficacy analysis population was mentioned in the Protocol and has been removed from the SAP as no specific analyses are planned based on the ITT population.

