9.4 Exploratory Analyses

The exploratory QFT endpoints (Section 4.3.3) will be analyzed in a manner similar to the primary endpoint.

The following summary results will be presented:

- Analyses based on the 4.0 IU/mL threshold for the initial QFT conversion where initial QFT conversion corresponds to the first QFT conversion after a negative (at or after Day 71) test result. These will be performed for both mITT and PP efficacy populations.
 - ↔ Overall initial QFT conversion rates and incidence rates, with 95% CIs for each treatment group.
 - A Kaplan-Meier plot by treatment group displaying the time to initial conversion based on 4.0 IU/mL threshold, displayed in months, measured from the vaccination date. Participants with no conversion will be censored at the date of data cut-off.
- Analyses based on a range of thresholds for the initial conversion from 0.36 IU/mL to 10 IU/mL using mITT population only.
 - Overall initial conversion rates with 95% CIs for each treatment group will be calculated for threshold values at each 0.01 increment from 0.36 IU/mL to 10

IU/mL. These pointwise estimates and 95% CIs will be plotted for the entire range of threshold values examined. A tabular presentation of the estimated conversion rates and 95% CIs will be displayed for threshold values of 0.36 IU/mL, 0.40 IU/mL, 1.0 IU/mL, 2.0 IU/mL, 3.0 IU/mL, 4.0 IU/mL, 5.0 IU/mL, 6.0 IU/mL, 7.0 IU/mL, and 10.0 IU/mL.

- ↔ Overall sustained conversion rates with 95% CIs for each treatment group will be calculated based on the subset of sustained conversion events identified in the primary analysis for which the initial conversion would have been "positive" using each alternative threshold value ranging from 0.36 IU/mL to 10 IU/mL. A tabular presentation of the estimated rates and 95% CIs will be displayed for the same threshold values as noted above for initial conversions.
- End of trial conversion rates with 95% confidence intervals for each treatment group, where end of trial conversion is defined as QFT conversion from a negative to positive (as per QuantiFERON-TB Gold Plus Package Insert) test result any time post-Day 71 with all QFT results after the initial conversion also positive.
- Kaplan-Meier plots for time to time to end of trial conversion, with tick marks to identify censored observations by treatment group
- Early QFT Reversion rates with 95% confidence intervals for each treatment group will be presented.

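### SAP 4.3.3 and 9.4 analyse the 4 IU/mL endpoint with a single cut-off rather than the protocol's change from <0.35 to ≥4 IU/mL, and censor its Kaplan-Meier curve at data cut-off rather than at the last QFT

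*SAP*

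**What the plan says.** Protocol Section 3 (Table 5) defines the endpoint as primary QFT conversion, "using an alternative definition of conversion as a change in IFN-γ concentration from <0.35 IU/mL to ≥4 IU/mL (initial conversion only". The synopsis, Section 4.1 and Section 9.4.1.2 give the same pair of values, and SAP Section 3 repeats the definition.

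SAP 4.3.3 works instead from a positive/negative status "derived based on a concentration cut-off value of 4 IU/mL in the QFT assay". The SAP's Table 1 algorithm is applied with 4 put in place of 0.35, and the section adds: "Primary (initial) QFT conversion corresponds to the first QFT conversion from a negative to positive test result". SAP 9.4 then lists "Analyses based on the 4.0 IU/mL threshold for the" initial conversion, starting from a negative result at or after Day 71, with no <0.35 condition. For the Kaplan-Meier plot of this endpoint it says: "Participants with no conversion will be censored at the date of data cut-off".

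The primary analysis does otherwise. SAP 9.1 and Appendix 6 censor a participant who never converts at the last non-missing QFT result before data cut-off.

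SAP Section 6, which records departures from the protocol, has one entry: "ITT efficacy analysis population was mentioned in the Protocol and has been removed from the SAP".

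**The concern.** With one cut-off at 4 IU/mL, a result of 1.2 IU/mL is negative. A participant who goes from 0.1 to 1.2 to 4.5 is then an initial converter at 4.5, although the package-insert rule already had that participant converting at 1.2. Read as a change between consecutive results, the protocol's definition would not count that path. The SAP therefore disagrees with the protocol and with its own Section 3, and a programmer following 4.3.3 may count more events than one following Section 3.

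The censoring rule is a second, separate matter. Conversion can be seen only when a QFT is done. Censoring a dropout at data cut-off keeps that person in the risk set, conversion-free, through a period with no test. This flattens the curve.

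**Working it through.** **The plan's own figure.** The only design figure is 118 events, for the primary endpoint. With hazard ratio 0.55, one-sided alpha 0.025, power 90% and 1:1 allocation, the Schoenfeld formula gives 4 × (1.960 + 1.282)² / (ln 0.55)² = 117.6, so 118, with power 90.1% at 118. It reproduces. No event number or power is stated for the 4 IU/mL endpoint.

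**The definitions side by side.** I applied four rules to example IFN-γ paths (IU/mL), all starting below 0.35 at Day 71:

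| Path | SAP 4.3.3 single cut-off | Preceding result <0.35, current ≥4 | First package-insert positive is ≥4 | Day 71 <0.35, any later ≥4 |
|---|---|---|---|---|
| 0.1, 0.2, 5 | event | event | event | event |
| 0.1, 1.2, 4.5 | event | none | none | event |
| 0.1, 1, 2, 4.2 | event | none | none | event |
| 0.1, 0.8, 0.2, 5 | event | event | none | event |
| 0.1, 3.9, 3.9, 3.9 | none | none | none | none |

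Direct jumps count under every rule. All differences come from paths through 0.35 to 3.99. On these paths the single cut-off agrees throughout with the Day 71 reading.

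**Why that agreement is only near.** Entry to the mITT population requires a package-insert negative at Day 71 or, failing that, the first later result (SAP 5.1). SAP Table 1 also calls a value negative if it is ≥0.35 but below 25% of Nil. With Nil at most 8.0, that allows entry values up to just under 0.25 × 8.0 = 2.0 IU/mL.

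**Possible effect on event counts.** Let s be the share of SAP events whose preceding result was not <0.35. The SAP then counts 1/(1 − s) times as many events as the consecutive-result rule. The documents give no value for s. Purely as assumptions, s = 10%, 25% and 50% give 1.11, 1.33 and 2.0.

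**Untested time from the censoring rule.** The input is the 5% average yearly loss in Protocol 9.2. If loss runs at a constant rate, the share of planned follow-up remaining over T years is (1 − 0.95^T) / (T × −ln 0.95), with −ln 0.95 = 0.0513.

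- T = 3: 0.1426 / 0.1539 = 0.927, so 7.3% is untested.
- T = 4: 0.1855 / 0.2052 = 0.904, so 9.6% is untested.

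This ignores conversions before dropout, which lower it, and the gap between last QFT and dropout, which raises it slightly.

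**Where this applies.** SAP 4.3.2 sets each participant's cut-off for the 36-month analysis at the Month 36 visit or the earlier discontinuation date. Dropouts are therefore not carried forward there. No such individual cut-off is given for the primary or final analysis.

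**The case against.** The best defence is that the protocol speaks of a change from <0.35 to ≥4 without saying that <0.35 must be the preceding result. Everyone analysed is in the mITT population or its per-protocol subset, so has already tested negative by the 0.35 rule. If <0.35 means that entry value, the single cut-off delivers the endpoint apart from the Nil clause. The words about initial conversion only could simply mean that no 3- and 6-month confirmation is needed. This stands as a possible reading, but the protocol does not state it. It would make the <0.35 condition almost redundant, and the SAP should say so if that is what is meant.

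On censoring, SAP 9.4 says the exploratory endpoints are analysed much like the primary one, and SAP 9.1 mentions participants censored at discontinuation. But 9.4 then gives its own explicit rule for this plot, and a specific rule would normally be followed over a general one.

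A reader might infer that the protocol's endpoint is never analysed. The documents do not support that, because direct jumps count under both rules and the Day 71 reading is open. A reader might also infer that the SAP counts different events from those behind the roughly 45% efficacy that Protocol 4.1 cites from the earlier trial. The documents do not say how that trial treated intermediate values, so this cannot be shown.

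**Conclusion.** The inconsistency is real and lies between current texts: SAP 4.3.3 and 9.4 on one side, the protocol and SAP Section 3 on the other, with nothing in SAP Section 6. Its size is unknown, because it depends on how many participants pass through 0.35 to 3.99 IU/mL and on which result <0.35 refers to. The multipliers above are illustrations, not estimates. Extra events in both arms need not move the hazard ratio.

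The censoring rule conflicts with SAP 9.1 and Appendix 6 for the primary and final analyses. At 5% yearly loss, untested time is about 7% (3 years) to 10% (4 years) of planned follow-up. A reader might quote the larger share ever lost, 1 − 0.95³ = 14.3% or 1 − 0.95⁴ = 18.5%. Those are proportions of people, not of time; they include people who converted before leaving, and the 3-year figure does not apply to the 36-month analysis.

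This is a minor point. The endpoint is exploratory, and SAP 7.8 treats inferential statistics for exploratory endpoints as descriptive. The primary test, its alpha and the 118 events are untouched.

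**What to change.** In SAP 4.3.3 and 9.4:

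- Define the event as a change from <0.35 to ≥4 IU/mL, with <0.35 applying to the immediately preceding QFT result. If the sponsor intended the Day 71 value, say so and list the single cut-off in Section 6.
- State how a participant with an intermediate result of 0.35 to 3.99 is handled and censored. This must settle whether such a participant stays at risk, and whether a path such as 0.1, 0.8, 0.2, 5 counts. Requiring the first package-insert positive to be ≥4 would drop that path, although it contains a change from <0.35 to ≥4.
- Keep the pure 4.0 cut-off within the 0.36 to 10 IU/mL range analysis, where 4.0 is already a tabulated value.
- Censor non-converters in this Kaplan-Meier plot at their last non-missing QFT, as in the primary analysis.

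The cost is SAP wording, one derived flag and possibly slightly fewer events for an exploratory endpoint.

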3 TRIAL OBJECTIVES AND ENDPOINTS

Objectives	Endpoints		
Primary			
To demonstrate the efficacy of BCG revaccination against sustained Mtb infection versus placebo in previously BCG vaccinated QuantiFERON (QFT) negative, healthy adolescents (event- driven analysis).	Sustained QFT conversion (at least 118 events) based on positive QFT test results (initial conversion and QFT-positive at 3- and 6-months post conversion [PC]).		
Secondary			
To evaluate the durability of efficacy of BCG revaccination against sustained Mtb infection versus placebo in previously BCG vaccinated QFT negative, healthy adolescents.	Sustained QFT conversion based on positive QFT test results (initial conversion and QFT-positive at 3- and 6- months PC) with a follow-up of 36- and 48-months post vaccination.		
To evaluate the safety and reactogenicity of BCG revaccination in previously BCG	Solicited adverse events (AEs) through 7 days post vaccination.		
vaccinated, QFI negative healthy adolescents.	Unsolicited AEs through 28 days post vaccination.		
	All serious adverse events (SAEs) and adverse events of special interest (AESIs) through Month 6.		
	Serious adverse drug reactions (Serious ADRs) through the end of the study.		
Exploratory			
To evaluate the efficacy and durability of efficacy of BCG revaccination against primary Mtb infection post vaccination versus placebo in previously BCG vaccinated, QFT negative healthy adolescents.	Primary QFT conversion at the time of primary endpoint analysis, and after a follow-up of 36- and 48- months post vaccination, using an alternative definition of conversion as a change in IFN-γ concentration from <0.35 IU/mL to ≥4 IU/mL (initial conversion only) [IU = international units]		
Exploratory (continued)			

Objectives	Endpoints
To evaluate the efficacy and durability of efficacy of BCG revaccination against primary and sustained Mtb infection post vaccination versus placebo in previously BCG vaccinated, QFT negative healthy adolescents, based on alternate QFT IFN-γ concentration cut-off values.	Primary and sustained QFT conversion at the time of primary endpoint analysis, and after a follow-up of 36- and 48-months post vaccination, based on a definition of primary and sustained conversions using exploratory IFN-γ concentration threshold values.

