4.3 Efficacy Endpoints

4.3.1 Primary Efficacy Endpoint

Mtb infection is defined in this protocol as QFT conversion from a negative to positive test result, as per the manufacturer's QFT-GIT package insert.

QFT assays will be performed at:

- Screening (used to determine eligibility),
- Day 71 or at the first in-person visit after Day 71 if Day 71 visit was missed or if Day 71 result was not available.
- Every 6 months (counting from Day 1) through Month 48
- Participants who have QFT conversions from a negative to positive test result will have an additional QFT assay three months post initial conversion (Day 84 PC visit).

The primary efficacy outcome measure is sustained QFT conversion in the mITT efficacy population (Section 5.1), defined as primary QFT conversion from QFT-negative to QFT-positive, and sustained

positive QFT tests at both 3- and 6-months after initial (primary) conversion. The initial positive QFT test must be observed after a negative QFT result at Day 71 or at the first in-person visit after Day 71 for which a QFT result is available if the Day 71 visit was missed or if the QFT result at the Day 71 visit was not available.

Due to the required washout period (Section 4.1) and the many Day 71 visits missed due to COVID (lockdown, site closure, etc.), the requirement for a negative QFT test result at Day 71 was extended to include results from the first in-person visit post Day 71. Therefore, throughout this document, Day 71 refers to the Day 71 study visit, or if missing, the first in-person visit post-randomization. Sustained conversion refers to three consecutive positive QFT results following the Day 71 negative QFT result as detailed above. After the initial conversion, a negative or indeterminate result at Post Conversion Day 84 and/or at the biannual visit following the initial conversion would disqualify the conversion event from being a sustained conversion. "Early QFT Reversion" is defined as a reversion from a positive QFT test result to a negative QFT test result at Post Conversion Day 84 or the biannual visit following the initial conversion.

Participants who initially convert to QFT positive at Day 71 will be excluded from the mITT analysis population and the primary endpoint analysis.

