Participants who initially convert to QFT positive at the Month 48 visit will be included in the count of primary QFT conversions but will not be included in the count of sustained conversions since the Month 48 visit is the final study visit.

To assess the vaccine efficacy on this primary endpoint, an event driven analysis will be utilized (Section 9.1).

The QFT qualitative classification (negative, indeterminate, or positive) at each visit will be determined by the laboratory as per the manufacturer's QFT-GIT package insert:

Nil (IU/mL)	TB Ag1 minus	TB Ag2 minus	Mitogen minus	QFT Result	
	Nil (IU/mL)	Nil (IU/mL)	Nil (IU/mL)		
≤8.0	≥ 0.35 and $\geq 25\%$	Any			
	of Nil		A	Desitive	
	Any	≥ 0.35 and $\geq 25\%$	Any	Positive	
		of Nil			
	<0.35 or ≥0.35	<0.35 or ≥0.35	≥0.50	Negative	
	and <25% of Nil	and <25% of Nil			
	<0.35 or ≥0.35	<0.35 or ≥0.35	< 0.50		
	and <25% of Nil	and <25% of Nil		Indeterminate	
>8.0	Any	•	•		

Table 1	1 QFT	Algorithm	from the	QuantiFERC	DN-TB Gold	l Plus Package	Insert
---------	-------	-----------	----------	-------------------	-------------------	----------------	--------

Ag= antigen.

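### At alternative QFT cut-offs the SAP applies the new threshold X only to the initial test and confirms at 0.35 IU/mL, so 'sustained conversion at X' can include participants who fell back below X

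*SAP*

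**What the plan says.** **Endpoint as stated.** Protocol section 3 (Table 5) lists primary and sustained conversion "based on a definition of primary and sustained conversions using exploratory" IFN-γ thresholds. The objectives table in SAP section 3 repeats it: "based on a definition of primary and sustained conversions using exploratory IFN-γ concentration threshold values". Protocol 9.4.1.2 likewise plans primary and sustained infection endpoints with conversion defined by thresholds other than 0.35 IU/mL.

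**Rule as specified.** SAP 4.3.3 says: "Each threshold cut-off will be used to assess initial conversion similarly to the procedure described in Table 1 for the 0.35 IU cut-off". It continues: "Sustained conversions for the various thresholds will be a subset of the sustained converters identified for the primary endpoint". SAP 9.4 does the same, basing the rates on the "subset of sustained conversion events identified in the primary analysis for which the initial conversion would have been" positive at the alternative threshold.

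**How those primary events were confirmed.** SAP 4.3.1 says: "Sustained conversion refers to three consecutive positive QFT results following the Day 71 negative QFT result as detailed above". The classification of each result "will be determined by the laboratory as per the manufacturer's QFT-GIT package insert". In SAP Table 1, positive means Nil of at most 8.0 IU/mL and at least one antigen-minus-Nil value of at least 0.35 IU/mL and at least 25% of Nil.

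**Declared changes.** SAP section 6 lists one change from the protocol, the removal of the ITT population. The threshold rule is not mentioned.

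**The concern.** No section applies X to the 3- or 6-month test. A participant whose first positive is 4.1 IU/mL and whose confirmatory results are both 0.4 is reported as sustained at 4.0 IU/mL, although two of the three results sit just above 0.35.

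This bears on why other cut-offs are explored. Protocol 4.1 refers to variability around the manufacturer's threshold. It also cites evidence that converters with any serial result between 0.2 and 0.7 IU/mL were at no higher risk of disease than nonconverters. That evidence concerns the whole series of results, not only the first. Under the SAP rule, a confirmatory result in that zone can still support sustained conversion at a high threshold.

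SAP 9.4 tabulates initial and sustained rates at the same thresholds. A reader who divides one by the other may take the result as persistence at X. It is persistence at the package-insert cut-off among those whose first positive reached X.

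**Working it through.** **Plan's own figure.** The documents give no figure for sustained conversion at an alternative threshold. The one related figure is the event target (SAP 7.2: VE 45%, so HR 0.55; one-sided alpha 0.025; 90% power; 1:1 allocation). Schoenfeld's formula gives

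D = 4 × (1.960 + 1.282)² / (ln 0.55)² = 4 × 10.507 / 0.3574 = 117.6, which rounds up to 118.

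Power at 118 events is 90.1%. The target is reproduced and is not in question.

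**The two rules.** Take the initial, 3-month and 6-month results as (a, b, c), with the Nil and mitogen conditions met.

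- SAP rule (4.3.3, 9.4): a, b and c all ≥ 0.35, and a ≥ X.
- All-three rule: a, b and c all ≥ X.

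Every X in the scan exceeds 0.35, so any series that meets the all-three rule also meets the SAP rule. The SAP count can therefore only equal or exceed the all-three count. The extra events are those with a ≥ X and b or c between 0.35 and X. That band is 0.36 − 0.35 = 0.01 IU/mL wide at the lowest threshold and 10 − 0.35 = 9.65 IU/mL wide at the highest.

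**Invented series at X = 4.0 IU/mL:**

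| Initial / 3-month / 6-month | SAP rule | All-three rule |
|---|---|---|
| 4.1 / 0.4 / 0.4 | counted | not counted |
| 4.5 / 5.0 / 1.0 | counted | not counted |
| 4.5 / 4.2 / 4.1 | counted | counted |
| 2.0 / 5.0 / 6.0 | not counted | not counted |
| 4.5 / 0.2 / 5.0 | not counted | not counted |

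**Size of the overcount (assumed inputs).** Let q be the share of SAP-counted events with both confirmatory results ≥ X. The overcount factor is 1/q.

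| q | 0.9 | 0.8 | 0.7 | 0.6 | 0.5 |
|---|---|---|---|---|---|
| 1/q | 1.11 | 1.25 | 1.43 | 1.67 | 2.00 |

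**Effect on vaccine efficacy (assumed inputs).** On a simple ratio of rates,

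VE(all three) = 1 − (1 − VE(SAP)) × q(BCG) / q(placebo).

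Taking VE(SAP) = 45% for illustration:

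- q equal in both arms (0.7 and 0.7): 1 − 0.55 × 1 = 45%, no change.
- q(placebo) 0.8, q(BCG) 0.6: 1 − 0.55 × 0.75 = 58.75%, about 59%.
- q(placebo) 0.6, q(BCG) 0.8: 1 − 0.55 × 1.333 = 26.7%, about 27%.

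**The case against.** **The SAP is open about its rule, and the protocol does not forbid it.** Protocol 8.1.1 leaves cut-off details to the SAP, and the SAP states the rule in two sections. No section says in terms that all three tests must reach X. That stands: this is a mismatch with the natural reading of the endpoint, not a breach of an explicit rule. The label and the silence in section 6 remain to be put right.

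**Varying only the first value serves a stated aim.** Protocol 4.1 justifies other thresholds mainly by QFT conversion as a surrogate for infection and a correlate of disease risk. The height of the converting test is relevant to that. This supports keeping the current rule as one output, but not naming it sustained conversion at X.

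**The endpoint is exploratory.** SAP 7.8 treats inference on it as descriptive only. That stands and limits the severity.

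Three stronger readings are tempting, and the documents do not support them.

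- *The sustained rates cannot be compared with the initial rates.* They can. Every SAP sustained event at X has an initial test positive at X, so the events are nested. The ratio is interpretable once it is described correctly.
- *An all-three rule would also recover participants who cross X late.* It would not: 2.0 / 5.0 / 6.0 fails both rules at X = 4.0. Protocol 8.1.1 and Table 4 provide one extra QFT, timed from the package-insert conversion, so the 3- and 6-month pattern cannot in general be rebuilt from a later crossing.
- *The misclassification is known to be large.* A lognormal model with assumed medians of 1 to 4 IU/mL, log SD 1.3 and within-person correlation 0.5 to 0.85 puts the share of SAP-counted events at 4.0 IU/mL with a confirmatory value below 4.0 anywhere from 27% to 79%. None of those inputs is in the documents, and the width of the range comes from the assumptions.

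**Conclusion.** The point holds as a minor correction to an exploratory endpoint. As written, the SAP's sustained rates at X describe package-insert sustained conversion with an initial test positive at X. They equal or overstate the number of participants with all three results positive at X. The direction follows from the definitions alone. The size cannot be derived, because the documents give no IFN-γ values at the 3- and 6-month tests.

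A reader might infer that the vaccine-efficacy picture across thresholds is biased. That does not follow: efficacy moves only if the share confirmed at X differs between arms, and nothing in the documents says that it does. The 59% and 27% figures show sensitivity to assumed shares and are not predictions.

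The primary and durability analyses, the 118-event trigger and the 4 IU/mL endpoint defined on initial conversion only are untouched.

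**What to change.** - In SAP 4.3.3 and 9.4, define sustained conversion at X as the initial conversion test, the PC Day 84 test and the next biannual test all positive under Table 1 with X in place of 0.35. Alternatively, report this alongside the current rule. Every primary sustained converter has these three results by definition, and SAP 4.2.3 already lists quantitative QFT results by participant.
- Label the current rule *package-insert sustained conversion with initial test ≥ X*, and list it in SAP section 6 as a difference from the protocol.
- State as a limitation that neither rule captures participants whose first package-insert positive is below X and who cross X later, because no further 3-month test is scheduled from that later crossing.

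The cost is SAP wording and programming, with no new data collection. The downside is fewer events and wider intervals at high X.
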